## **BACKGROUND**

Protocol V 1.6

- **A.** Opioid use disorder (OUD) is highly associated with comorbid chronic pain. Opioid use disorder, a condition affecting 2 million persons in the United States, is defined by a pattern of opioid use with significant personal, professional, and social consequences. In addition to being highly associated with health outcomes such as overdose related to opioid use, OUD is also highly related to poor general health, low quality of life, and debilitating chronic pain. Among patients receiving medications for OUD, over half report at least moderate chronic pain, and more than a quarter report at least severe chronic pain. Evidence suggests that poorly controlled chronic pain may impact OUD outcomes, likely mediated through increased opioid craving to relieve pain and/or reduce depression and anxiety symptoms. B. New and innovative treatments for chronic pain are needed. Despite the burden of chronic pain, established treatments are ineffective, laden with severe side effects, or inaccessible. Opioid therapy is common but ineffective for the treatment of chronic pain and, moreover, carries significant risk of severe adverse events including overdose. In these reasons, non-pharmacologic treatment for chronic pain is recommended by numerous clinical practice guidelines. However, numerous barriers, including local availability and perceived lack of efficacy, impede access to non-pharmacologic treatment options. For these reasons, studies of new and innovative treatments are needed.
- **C. Barriers and facilitators to non-pharmacologic treatment for chronic pain among persons with OUD.** Accessing non-pharmacologic treatment among persons with OUD is further compounded by several unique barriers, including stigma and federal requirements requiring persons to visit MMTPs daily or very regularly.  Integrating on-site non-pharmacologic treatments for chronic pain into MMTPs is an innovative strategy to reduce systemic and logistical barriers to treatment of chronic pain and has the potential to reduce stigma. 
- **C. VR treatments for chronic pain.** VR treatments represent a relatively new and highly innovative treatment paradigm for chronic pain. VR treatments already have established efficacy in mood disorders, anxiety, phobias, and acute pain.  Multiple systematic reviews have established that VR interventions for the treatment of chronic pain are promising, but interventions to date are heterogenous and further study is needed to demonstrate efficacy.  For example, immersive VR in a virtual environment tends to be associated with higher pain reduction and greater satisfaction.  Relevant to this application, the immersive VR intervention (RelieVRx) proposed for use in the current study was tested in a sample of 179 adults with chronic low back pain and shown to be effective in an 8-week trial in reducing pain and improving sleep, mood, and stress; most changes persisted up to 3 months. 
- **D.** VR treatments have been used in substance use disorders, and early evidence suggests VR treatments can be effective in OUD. A recent systematic review concluded that VR treatments can provide benefits in substance use disorder treatment, mainly owing to the ability of a therapeutic, immersive environment. In persons with nicotine addiction and alcohol use disorder, VR treatments found mixed to positive results on a number of nicotine and alcohol outcomes, including decreased craving. A recent non-randomized pilot study of a VR meditative intervention with 15 persons on methadone for OUD showed reductions in pain, opioid craving, anxiety, and depression in addition to reduced saliva cortisol, and changes in brain activation in the postcentral gyrus region of the brain on pain related tasks.
- **E.** Immersive mindfulness VR can lead to improved pain and OUD outcomes through its targeted effects on stress and inflammation. Mindfulness exercises have been associated with a myriad of positive outcomes that are relevant to the current study, including improved quality of life, pain interference, mood and anxiety symptoms, sleep quality, opioid craving, and opioid use.  We propose

these positive outcomes work through targeted effects on stress and inflammation, as mindfulness therapies have been associated with reductions in both patient reported stress and inflammation and in biomarkers linked to stress (such as cortisol) and inflammation (such as C-reactive protein and cytokine levels). 45,50–52 Reductions in both stress and inflammation, in turn, are associated with improved pain and OUD outcomes. 53–56

**F. Summary.** Chronic pain is highly prevalent in patients with OUD, and new and innovative treatments and onsite treatment paradigms are needed. We propose an innovative, on-site immersive mindfulness VR treatment targeting stress and inflammation to improve pain and OUD outcomes. The proposed trial will be the first pilot RCT study of VR treatment in a methadone maintenance treatment program (MMTP), and has the potential for widespread application.

## STUDY DESIGN

Overview. In a 6-week pilot RCT, we will assess the feasibility and preliminary efficacy of an immersive mindfulness VR treatment (RelieVRx) versus a non-immersive sham VR control (sham VR) for the treatment of pain and OUD. We will recruit 40 adults with OUD and chronic pain enrolled in an MMTP and randomize 1:1 to RelieVRx vs sham VR. Over 6 weeks, participants in both groups will participate in 20-30 minute VR sessions twice per week at the MMTP. Over the course of the study, the research team will conduct pain and psychological assessments at baseline, 3 weeks, and at the study conclusion at 6 weeks. We will also explore changes in stress and inflammatory saliva and blood biomarkers at baseline, 3 weeks and 6 weeks. To assess feasibility, we will examine recruitment and retention and assess patient satisfaction. Our preliminary efficacy co-primary outcomes are (1) change in pain intensity and (2) change in opioid craving between treatment groups at 6 weeks. Secondary outcomes will include changes in pain interference, physical functioning, depression, anxiety, sleep quality, illicit opioid use, and prescription opioid use. In a separate aim, we will also explore changes in stress and inflammatory markers over the course of the trial.

Setting and Participants. We will recruit and conduct study visits at one Montefiore Opioid Treatment Program (OTP). Montefiore has the largest network of OTPs in New York State. Three of the five Montefiore OTPs comprise the Montefiore Division of Substance Abuse (DoSA) Wellness Centers; in total, these sites serve approximately 3,000 individuals. Electronic health data indicates that of 945 people with a chronic pain diagnosis who are on methadone for OUD, 555 (59%) are Male, mean age is 58.3, 566 (60%) are Hispanic, 170 (18%) are Black, and 140 (15%) are White.

Participants: We will enroll 40 participants. As the narration of the VR device is only provided in English at this time, we require English proficiency for this pilot trial. Inclusion criteria: 1) ≥18 years old, 2) English proficiency; 3) receiving methadone treatment for DSM-5 confirmed OUD in the Montefiore network for at least 12 weeks, with no dose change in 14 days to ensure treatment stability; 4) chronic pain of at least moderate pain severity (score ≥4 on the Pain, Enjoyment of Life, and General Activity (PEG) scale); 5) willingness to participate in all study components; and 6) ability to provide informed consent, assessed using consent teach-back. Exclusion criteria: 1) conditions that could make participation in VR hazardous or cause adverse effects (current or prior diagnosis of epilepsy, seizure disorder, dementia, or migraines, any medical condition predisposing to nausea or dizziness, hypersensitivity to flashing light or motion), 2) conditions that could prevent proper use of the VR headset (stereoscopic vision or severe hearing impairment, or injury to eyes, face, or neck that prevents use of the VR headset), and 3) acute exacerbation of psychiatric conditions that preclude the ability to participate in the study. Pregnant patients are NOT excluded from the trial as there are no contraindications to their use of a VR device, but we are not specifically targeting pregnant patients for this study nor are we testing for pregnancy.

**Recruitment, Screening, and Randomization**. Recruitment will be active and passive in the OTP. Based on our team's prior DoSA trials and the scope of this current project, we anticipate enrolling 1-2

participants weekly. Research staff will enroll from one DoSA site for the duration of the trial; we will plan our recruitment strategy in conjunction with other IMPOWR-ME trials as to not recruit from the same pool of patients at a site at the same time. We expect retention of approximately 85% based on our groups prior DoSA trials.  **Screening:** After obtaining written consent, we will administer a screening questionnaire. Potentially eligible subjects will then complete a written informed consent process including discussion of procedures and risks and benefits before being randomized. Consent will occur in a private area of the OTP. **Randomization**: Randomization will occur using block randomization (blocks

of 4) to two conditions in a 1:1 ratio.

**Description of** intervention and control. Both intervention and control arms will utilize a Pico G2 head-mounted VR device with preinstalled software. RelieVRx incorporates evidence-based principles of cognitive behavioral therapy and mindfulness to provide pain neuroscience education and to train users on evidence-based pain and stress management strategies with interactive and immersive exercises and experiences. In total, RelieVRx combines biopsychosocial pain education, diaphragmatic breathing training, relaxation exercises.

| Table 1. Overview of Dat
Domain | Measure  | Source        |
|------------------------------------|--|---------------|
| Feasibility Outcomes               | 1 Transmit   | Source        |
| Percent screened                   | Proportion of total participants contacted who are screened  | RL            |
| Percent consented                  | Proportion of total participants screened who consent  | RL            |
| Percent retained                   | Proportion of total participants consented who complete  | RL            |
| r creent retained                  | study  |               |
| Patient satisfaction               | Global impression of change scale   | S             |
| Preliminary Efficacy Out           |  |               |
| Pain intensity (co-
primary)    | PEG,  PROMIS Pain Intensity subscale   | S             |
| Opioid craving (co-
primary)    | Opioid Craving Visual Analog Scale    | S             |
| Quality of life                    | PROMIS Physical Functioning, PROMIS PROPr Fatigue,
Cognitive Function, Social Function   | S             |
| Stress                             | Perceived stress scale   | S             |
| Pain interference                  | PROMIS Pain Interference Subscale, 61 PEG   | S             |
| Pain history and                   | Pain screening questions, Michigan pain body map  , use   | S             |
| characteristics                    | of medications and treatments, chronic pain acceptance,  pain self-efficacy  , pain catastrophizing                   |               |
| Mood symptoms                      | PROMIS PROPr Depression, Anxiety    | S             |
| Sleep quality                      | PROMIS Sleep Disturbance 6A + Sleep Duration    | S             |
| Illicit opioid use and             | Modified Addiction severity index  , Narcan use and   | S             |
| substance use                      | overdose   |               |
| Prescription opioid use            | Opioid prescriptions, including methadone dose   | S, EMR
PMP |
| Sociodemographics                  | Age, gender, insurance, race/ethnicity, education, marital status, socioeconomic status, social support  , social risk assessment questionnaire | S             |
| Perceived discrimination           | Adapted perceived discrimination scale    | S             |
| Mindfulness                        | Mindful attention awareness scale   | S             |
| Technology Attitudes               | VR Knowledge, Media and Technology Use and Attitudes subscale   | S             |
| Stress and Inflammation            |  |               |
| Cortisol                           | Morning salivary cortisol, serum morning cortisol  | L             |
| C-reactive protein                 | Serum CRP  | L             |
| Cytokine panel                     | Serum cytokines  | L             |
| Before/After VR Surveys            |  |               |
| Pain                               | Pain intensity score   | S             |
| Mood                               | Brief Mood Introspection Scale    | S             |
| Mindfulness                        | State Mindfulness Scale   | S             |
| Immersion & Distraction            | Adapted Immersion Scale  , Adapted Distraction Scale   | S             |

and executive functioning and attentional games to strengthen pain coping skills. RelieVRx is typically delivered in a 56-day program through daily virtual experiences, with each experience lasting between 2 and 16 minutes; in this pilot study, we will conduct in-office virtual experiences twice weekly. Each session will last about 20-30 minutes and go through 1-5 virtual experiences. The sham VR control is a non-immersive set of 56 daily virtual experiences, tuned to the length of the RelieVRx. Control participants will similarly experience 1-5 virtual experiences in each 20-30 session.

**Data sources, measures, and management.** Study assessments will take place onsite at the OTP at weeks 0, 3, and 6 and last 30-60 minutes. Participants will receive \$50 compensation at each study assessment. We will track the number of patients screened, eligible, consented, and retained. During assessments, participants will answer surveys and submit saliva and blood. In addition, we will extract information from the Montefiore EMR, SMART EMR (methadone dosage), and from the New York State Prescription Monitoring Program (PMP). Study measures are listed in Table 1; where possible we align our measures with IMPOWR CDEs and with IMMPACT recommendations for study of chronic pain. All measures will be examined at each study visit, at 0, 3 and 6 weeks. All study assessment data will be managed in REDCAP, a well-established, HIPAA-compliant web-based surveying platform and database. During twice weekly VR sessions, we will also conduct before and after surveys to ask about experiences during VR exercises not taking more than 5 minutes; these will be paper based, scanned, and uploaded to Montefiore BOX, a HIPAA-compliant online cloud storage service. A portion of blood will also be bio-banked to facilitate future biomarker analyses. We will conduct an optional qualitative interview exploring experiences in the trial at the conclusion of the trial; participant interviews will be recorded and transcribed for analysis.

**Informed Consent.** The RA will screen all potential participants for inclusion and exclusion criteria in a private area of the MMTP. First, we will obtain written consent to administer a screening questionnaire. Screening questionnaire questions will focus on inclusion and exclusion criteria, pain history, and also ask about prior use of virtual reality devices. The initial screening questionnaire will take 15 minutes. Participants will not be reimbursed for the screening questionnaire. Written consent and the initial screening questionnaire will occur in a private area of the MMTP.

Potentially eligible subjects will then complete a written informed consent process with HIPAA authorization including discussion of procedures and risks and benefits before being randomized. Consent will occur in a private area of the OTP. The RA will perform consent teach-back to assure that participants are aware of the details of the consent. Participants who give consent and are randomized will then complete the first study visit at a convenient time. Participants will be reimbursed \$50 for their participation at each study assessment. If they choose to participate in the optional qualitative component, they will be reimbursed an additional \$30.

Tests and procedures, including blood draws and saliva samples, performed at study assessments will not be billed to participants.

Patient privacy protection. We will strip patients' protected health information from all data before conducting analyses. As in prior studies we have conducted, we will have a "name-based" and an "ID-based" identification system that will remain separate. In the name-based system, all documents that have patient identifiers will be filed together. Some of these documents will have participants' signatures (e.g., consent forms). In the ID-based system, all documents that do not include identifying information or signatures will use participants' unique study IDs (rather than names) and will be filed together. All forms will contain either a "name-based" or an "ID-based" identifier, but never both. There will be only one electronic document that links participants' names to their study IDs; only the study staff will have access to this document, which will be password protected and kept on password-protected servers.

Study data will be kept in a password-protected, encrypted file on password-protected servers that are backed up daily. No one but the study team will have access to study data. Publication or presentation of study results will not include information that would allow for identification of providers or patients.

**Analytic plan.** Feasibility: Feasibility outcomes will be measured as proportions. Preliminary Efficacy: To examine the association between treatment arm and the co-primary outcomes, we will use separate 2-level mixed-effects linear regression model with the treatment arm as a mixed effect with participant-specific random intercepts to account for hierarchical data. The difference in trends of pain intensity and opioid craving will be represented by the time-by-arm interaction. For secondary outcomes and stress and inflammation exploratory outcomes, we will use a similar strategy; where outcomes are dichotomous, we will use 2-level mixed effects logistic regression models.

We will use thematic analysis to analyze transcripts in the qualitative study.

**Power analysis**. The primary purpose of this study is to test feasibility and to generate preliminary data for a future R01 application. We are able to enroll 40 participants in the pilot RCT given our resources and given the time of this study. We base our conservative power analysis on t-tests of change in our pain intensity preliminary efficacy outcome and use effect size estimates from a study of RelieVRx. In that study, the pre-post difference in pain intensity was 2.2 in the treatment group and 1.2 in the control group. Given the effect size of d=0.49, and 20 participants in each arm, we will have 70% power to detect a difference of this magnitude or larger. We expect to have greater statistical power using mixed effects linear regression models with repeated measures over time.

**Risks/Benefits**. We expect the major risks to be associated with the VR technology. VR can sometimes cause "cybersickness" in some patients, especially when playing or experiencing fast moving games or videos. RelieVRx is a much less intense program designed to minimize these sensations. In the clinical trial of RelieVRx, about 10% of participants reported some nausea and/or motion sickness, but these symptoms were temporary and none decided to terminate their use of the technology because of adverse events. In our preliminary data of 20 patients, no patients have reported any issues with cybersickness. Nonetheless, this will be an important risk to discuss with patients.

Another risk is breach of confidentiality of patient data. Such a breach is unlikely, because all study staff will be trained in confidentiality and secure data management, and the data collected as part of this study will be stripped of protected health information.

In the major clinical trials of RelieVRx, both intervention and sham VR groups had reduced pain at the end of the trial, with the magnitude being larger in the intervention arm. However, this trial is shorter and some of the parameters are not the same, including the number of weeks of the intervention. Therefore, it is possible, but not certain, participants will receive a direct benefit.

**Data Safety Monitoring Plan**. Monitoring of recruitment and retention, adverse events, protocol deviations, and protocol violations will be ongoing by the Principal Investigator. Additionally, the PI and co-investigators will meet every 2 months in person to discuss recruitment, retention, data quality, and any adverse events. Together, they will make corrective plans as necessary. No interim analyses are planned for this pilot trial.

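### Fixed blocks of 4 at one site, with no concealment or staff masking described, leave on average one third of assignments certain to anyone who knows the earlier ones

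*Combined protocol and SAP*

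**What the plan says.** Under Study Design, the paragraph on recruitment, screening and randomization gives the method: "Randomization will occur using block randomization (blocks" "of 4) to two conditions in a 1:1 ratio". The size is 4, with no variation and no strata. The same section sets the total ("We will enroll 40 participants") and the number of sites ("Research staff will enroll from one DoSA site for the duration of the trial"). On pace, it says "we anticipate enrolling 1-2" participants a week.

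Consent precedes allocation: "Potentially eligible subjects will then complete a written informed consent process including discussion of procedures and risks and benefits before being randomized". The Informed Consent section gives eligibility work to the research assistant: "The RA will screen all potential participants for inclusion and exclusion criteria in a private area of the MMTP". Treatment is delivered at the clinic: "in this pilot study, we will conduct in-office virtual experiences twice weekly". The active program is immersive and the sham is not, although both run on the same headset model.

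The documents do not say who generates or keeps the sequence, how the next assignment is hidden, or whether the staff who recruit, run sessions or collect assessments are masked.

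**The concern.** In a block of 4 with two places per arm, the last assignment always follows from the first three. Sometimes the third and fourth both follow from the first two. Anyone who knows the block size and has tracked earlier assignments can therefore foresee some allocations before deciding whether, or when, to bring in the next candidate. The conditions for tracking are favourable here: one site, apparently one running list, a small team, slow enrolment, and sessions on the premises with two programs that differ in immersion.

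If entry were timed or steered on that knowledge, the arms could differ systematically at baseline. Pain intensity and opioid craving, the co-primary outcomes, both come from participant surveys (Table 1). The analysis rests on the time-by-arm interaction, so a difference in starting level is not itself the estimated effect. It can still act indirectly. Entry requires a PEG score of at least 4, and an arm loaded with people at an unusually severe point may improve more through regression to the mean alone. The Informed Consent section also places the first study visit after randomization, so baseline scores are collected once allocation exists. That adds to the reasons for describing concealment and masking.

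**Working it through.** **Inputs.** Block size 4, ratio 1:1, 40 participants, one site and 1-2 enrolments a week, all from Study Design. No strata are stated, so I assume one list of 40 / 4 = 10 complete blocks. The documents give no predictability figure, so there is none to reproduce. All results below assume an observer who knows every earlier assignment.

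**Pace.** A block takes 4 / 2 = 2 to 4 / 1 = 4 weeks to fill.

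**Certain assignments in a block of 4.** There are 6 equally likely orders with two of each arm. Two of them (AABB, BBAA) fix the last two places. The other four fix only the last.

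- Expected number certain = (2 × 2 + 4 × 1) / 6 = 1.33 of 4 = 33.3%.
- Minimum 1 of 4 (25%); maximum 2 of 4 (50%).

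**Scaled to 40.** Number certain = 10 + Binomial(10, 1/3).

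- Mean = 10 + 10/3 = 13.3.
- Central 95% range 11 to 16; possible range 10 to 20.
- Probability of 14 or more = 44%.

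**Best guess in a block of 4.** The observer names the arm with more places left and tosses a coin when they are equal.

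- Place 1: 1/2.
- Place 2: 2/3.
- Place 3: (1/3 × 1) + (2/3 × 1/2) = 2/3.
- Place 4: 1.
- Average = (0.500 + 0.667 + 0.667 + 1.000) / 4 = 70.8%, against 50% with no information.

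**Varied blocks.** These were simulated as lists of 40. The observer knows the set of possible sizes but not the current one, and updates exactly on all past assignments. The sizes are my illustration and do not come from the documents.

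| Scheme | Certain in advance | Best guess correct | Lists ending unequal |
|---|---|---|---|
| Fixed 4 | 33% | 71% | none |
| 4 and 6 mixed | about 5.5% | 69% | about 24%, all 21 vs 19 |
| 4, 6 and 8 mixed | about 2.3% | 68% | about 27%, nearly all 21 vs 19, at most 22 vs 18 |

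Repeat runs moved the certain share by a few tenths of a percentage point.

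**What varied blocks leave in place.** The advantage over a coin toss is 71 - 50 = 21 points with fixed blocks, 69 - 50 = 19 with sizes 4 and 6, and 68 - 50 = 18 with 4, 6 and 8. So 18/21 to 19/21, or roughly 86-90%, of the guessing advantage remains.

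**The case against.** The strongest reply is that the risk depends on something the documents do not establish. Prediction needs staff who know past allocations. Both arms use the same headset model with software already installed, and the sham is matched to the active program in length, which is compatible with staff not knowing the arm. A reader might infer from the silence that staff are unmasked, but the text does not say so, and it does not say they are masked either. This part of the reply stands, and the point is conditional for that reason.

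Second, steering does not require certainty, and varied blocks barely reduce the best guess. This also stands. The gap underneath is undescribed concealment and masking, so block size cannot be the whole remedy.

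Third, consent already comes before randomization in the plan. That is true. The addition is a system that enforces the order and keeps the next assignment hidden until then.

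Fourth, this is a pilot whose main purpose is feasibility, and blocks of 4 are a legitimate way to reach exactly 20 per arm. That limits the weight of the point. It does not remove it, because the efficacy estimates are meant to support a later grant application and the change is small.

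**Conclusion.** The point holds in conditional form. If enrolling staff know the block size and all earlier assignments, on average one third of allocations (13 of 40) are certain and the best guess is right 71% of the time. The figures assume one unstratified list; stratification, which is not mentioned, would change the counts.

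Three stronger readings are tempting and should not be adopted.

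- A reader might take one third as a ceiling. It is the mean: at least 10 and at most 20 of 40 are certain.
- A reader might infer that every efficacy outcome is self-reported. Table 1 also draws prescription opioid use from the medical record and the prescription monitoring program, and the exploratory biomarkers are laboratory measures. The statement is right for the two co-primary outcomes.
- A reader might treat a baseline imbalance as if it were the treatment effect. The planned model estimates a difference in trends, so only an indirect route remains, and the documents give no figures from which to size that bias in outcome units.

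The plan's stated method can be replaced by a better one at trivial cost. It should be changed, as a cheap improvement rather than as a defect that invalidates the trial.

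**What to change.** Replace the fixed block size with randomly varied sizes, for example 4 and 6, or 4, 6 and 8, and keep the sizes out of any text that enrolling staff see. Have someone with no part in enrolment generate the list and hold it in REDCap, which the trial already uses. Set the system to release each assignment only after eligibility and consent have been recorded.

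Varied blocks remove most of the certainty but little of the guessing advantage. So also keep earlier assignments from the staff who screen and consent, where existing staffing allows, and state in the protocol which roles know the arm. If staff are already masked, saying so costs one sentence.

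The cost is one regenerated list and a few sentences. The downside is losing a guaranteed 20 versus 20: about a quarter of lists end slightly unequal, usually 21 versus 19 and at most 22 versus 18 in simulation.

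### Overdose and naloxone use have the participant survey as their only named source, so this measure misses events after the last attended visit and cannot record a death

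*Combined protocol and SAP*

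**What the plan says.** Table 1 places overdose and naloxone use in the row for illicit opioid use and substance use ("Modified Addiction severity index 70 , Narcan use and" overdose). The Source column for that row reads S, the survey. The following row, "Opioid prescriptions, including methadone dose", has S, EMR and PMP, and it is the only row in the table with a record source of that kind.

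The paragraph on data sources, measures, and management sets the timing: "All measures will be examined at each study visit, at 0, 3 and 6 weeks". It also says "In addition, we will extract information from the Montefiore EMR, SMART EMR (methadone dosage), and from the New York State Prescription Monitoring Program (PMP". It does not list overdose or death among the items to be extracted.

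On follow-up, the recruitment paragraph says "We expect retention of approximately 85" per cent. On safety, the Data Safety Monitoring Plan says "Monitoring of recruitment and retention, adverse events, protocol deviations, and protocol violations will be ongoing by the Principal Investigator", and it adds that the investigators will meet every two months and discuss any adverse events. It does not define an adverse event, name where adverse events are found, or say how events are found in participants who stop attending. The documents mention neither death nor follow-up of people who drop out.

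**The concern.** A survey answered on site depends on the participant coming back. Someone who overdoses and does not return adds nothing to this measure, and a death can never be self-reported. In people with opioid use disorder it is plausible that leaving the study is related to relapse, so the unobserved participants may be those at higher risk.

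The stake is the safety statement the pilot carries forward. The Power analysis paragraph says the study is meant to generate preliminary data for a later grant application. A report of no overdoses that rests on this item would describe those who kept attending, not all who were randomised. If attendance differed between the RelieVRx and sham arms, counts by arm would be distorted as well. The plan already opens the Montefiore EMR for these participants, so a source that does not depend on attendance is at hand but is not assigned to this item.

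**Working it through.** The plan states no overdose rate or event count, so there is no figure to reproduce. The check compares the named sources and then sizes the gap under labelled assumptions.

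**Which named route would find an overdose or death in someone who stops attending?**

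| Route | What the protocol assigns to it | Reaches a non-attender? |
|---|---|---|
| Survey at weeks 0, 3, 6 (Table 1) | Overdose and naloxone use | No; cannot record a death |
| Surveys before and after each VR session (Table 1) | Pain, mood, mindfulness, immersion and distraction | No; overdose not listed |
| Montefiore EMR | General extraction; Table 1 uses it only for prescription opioids | It could, but overdose and death are not named |
| SMART EMR | Methadone dosage | Not assigned to this |
| Adverse-event monitoring by the Principal Investigator | Adverse events, no source named | Not stated |

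**Inputs.** Randomised: 40 (Participants). Retention: about 85% (Recruitment, Screening, and Randomization). Survey times: weeks 0, 3 and 6. Not in the documents, so assumed: the ratio k of six-week overdose risk in non-completers to that in completers, the time of leaving, and a constant risk over the six weeks.

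**Step 1: non-completers.** 0.85 × 40 = 34 retained; 40 − 34 = 6 not retained.

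**Step 2: share of non-fatal events the survey misses.** Events in completers are proportional to 34 and in non-completers to 6k. If non-completers leave before the week 3 survey, all their events are missed and the share is 6k / (34 + 6k). If they leave just after it, only the second three weeks are missed, which is half of that.

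| k (assumed) | Leave before week 3 | Leave after week 3 |
|---|---|---|
| 1 | 6/40 = 15.0% | 7.5% |
| 2 | 12/46 = 26.1% | 13.0% |
| 3 | 18/52 = 34.6% | 17.3% |
| 5 | 30/64 = 46.9% | 23.4% |

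Only the first row needs no assumption of excess risk. The others show how fast the share grows.

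**Step 3: absolute size.** With an assumed six-week risk r that is the same for everyone, the expected number of events among the 6 is 6r, and the chance of at least one is 1 − (1 − r)^6. For r = 1%, 2%, 5% and 10%, the expected numbers are 0.06, 0.12, 0.30 and 0.60, and the chances are 5.9%, 11.4%, 26.5% and 46.9%. These are the missed events if all 6 leave before week 3, and an upper bound otherwise.

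**Step 4: deaths.** The survey captures none, whatever the retention.

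**The case against.** Three stronger readings are tempting, and the documents do not support them.

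- A reader might infer that the trial as a whole will miss every fatal overdose and every event in dropouts. That is true of the survey item only. Adverse-event monitoring is described as ongoing and is not limited to surveys or to people who attend. Participants are scheduled on site twice a week, are established patients of the network, and have an EMR that the team will open.
- A reader might infer that overdose is excluded from adverse-event monitoring. The plan is silent on this; it does not exclude it. The Background remark that opioid therapy "carries significant risk of severe adverse events including overdose" concerns harms of opioid treatment for pain and does not define adverse events for this trial.
- A reader might infer that overdose has been misfiled as an efficacy endpoint because its row falls under the heading beginning "Preliminary Efficacy Out". The same block holds sociodemographics and technology attitudes, so it works as a list of data collected. The study overview does not name overdose among the secondary outcomes.

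The size can also be challenged. The larger shares in the table rest on chosen risk ratios. At an assumed 1% to 2% risk, only 0.06 to 0.12 events are expected among the 6. A small pilot says little about overdose in any case: the one-sided 95% upper limit after no events is 1 − 0.05^(1/34) = 8.4% with 34 people and 1 − 0.05^(1/40) = 7.2% with 40. Distortion between arms is hypothetical, since the plan names no overdose comparison.

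All of this limits the point without removing it. The other channels could find these events, but none is assigned to do so, and the session surveys do not ask about overdose. The case for the change rests on complete ascertainment of a serious event in everyone randomised. Gain in precision is not the reason for it.

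**Conclusion.** The point holds for the measure, and it is an inexpensive improvement to a stated method. Followed as written, the Table 1 item misses non-fatal overdoses and naloxone use after a participant's last attended visit and cannot record a death, although the Montefiore EMR extraction is already planned. About 6 of 40 participants are expected not to complete.

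Under equal risk in completers and non-completers and constant risk over time, 7.5% to 15% of non-fatal events would be missed, depending on when people leave. The share is larger if non-completers are at higher risk, but by how much cannot be settled from the documents. Whether the trial would learn of these events through adverse-event monitoring is left open: the wording is broad enough to include them, but no source is named that would find them in people who stop attending.

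**What to change.** 1. In Table 1, change the source for overdose and naloxone use from S to S, EMR.
2. In the data sources paragraph, state that overdose and death will be extracted from the Montefiore EMR for all 40 randomised participants, from randomization to week 6, whether or not they attend.
3. In the Data Safety Monitoring Plan, state that overdoses and deaths found from any source are recorded as adverse events.
4. In the Analytic plan, state that these counts will be reported by randomised arm.

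The cost is one table entry, a few sentences, and a few more minutes of chart review per participant. Two limits should be acknowledged. The Informed Consent section mentions a HIPAA authorization but its scope is not visible, so its coverage of these items must be confirmed. Events outside the Montefiore network would still be missed, and the report should say so.
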